9.2 Sample Size Determination

A sample size of N=45 subjects per group will provide at least 90% power to detect a between group difference in the proportion of subjects with at least a 5 mg/day HCe reduction from baseline in GC dose at Week 24 with A4 \leq ULN of at least 33%, assuming the placebo group has a response of 30% and the two-sided type I error is 0.05.

9.3 Populations for Analyses

The ITT Population will include all randomized subjects. The ITT Population will be the primary analysis set for analyzing demographics, baseline characteristics, and efficacy.

The mITT Population will include all randomized subjects who receive at least 1 dose of study drug (tildacerfont or placebo).

The PP Population will include all randomized subjects who have no major protocol deviations that would affect the analysis of efficacy data, defined as the following:

- Subject did not meet efficacy-based inclusion criteria (hormone levels, GC regimen)
- Subject met efficacy-based exclusion criteria (inadequate adherence to GC regimen, night-shift worker)
- Subject's adherence to study drug or the subject-specific GC regimen was <80% over the Treatment Period

Additional criteria may be specified in the SAP. The PP Population will be identified prior to database lock.

The mITT and/or PP Populations may be used for secondary analyses of the primary and secondary efficacy endpoints.

The Safety Population will include all subjects who receive at least 1 dose of study drug (tildacerfont or placebo), summarized by actual drug received. The Safety Population will be the primary analysis set for general and safety analyses.

The PK Population will include all subjects who receive at least 1 dose of tildacerfont and have at least 1 evaluable PK sample.

9.4 Statistical Analyses

9.4.1 General Considerations

All individual data will be listed as measured. All statistical summaries and analyses will be performed using SAS software (SAS Institute Inc, Cary, North Carolina, USA).

Unless otherwise specified, continuous adrenal biomarkers (A4, 17-OHP, ACTH) will be summarized using a 11-point descriptive statistics (i.e., n, mean, standard deviation [SD], median, 25% quartile [Q1], 75% quartile [Q3], minimum, maximum, geometric mean, geometric coefficient of variance [CV%], 95% confidence interval [CI] for geometric mean [including geometric mean ratio and its 95% CI]). Continuous data aside from (A4, 17-OHP and ACTH) will

be summarized using an 8-point descriptive summary (n, mean, SD, median, Q1, Q3, minimum, and maximum).

Categorical data will be summarized using the frequency of events and percentage of total events.

Data will be presented by treatment group. Changes in primary, secondary, and exploratory endpoints will be analyzed over time, with change from baseline summarized for each post-baseline time point measured.

All efficacy analyses will be conducted using the ITT Population as the primary analysis set and using a 2-sided alpha of 0.05.

For missing data, a retrieved dropout approach will be used in which missing endpoint data for subjects who discontinued early will be imputed using data collected from subjects after discontinuation of study drug.

Secondary and exploratory analyses that evaluate the change from baseline in all subjects after 52 weeks of tildacerfont treatment will combine the subjects randomized to tildacerfont Day 1 to Week 52 data with subjects randomized to placebo tildacerfont treatment data from Week 24 to Week 76.

Any changes to the protocol-specified analyses will be pre-specified in the SAP prior to database lock.

9.4.2 Analysis of the Primary Efficacy Endpoint

The primary efficacy endpoint is the absolute change from baseline in GC dose in HCe at Week 24. The null hypothesis is that there is no difference in the mean change from baseline to Week 24 in GC dose in HCe. The alternative hypothesis will be that there is a difference between the treatment groups. The ITT Population will be used for the primary analysis of the primary efficacy endpoint. The analysis of the primary endpoint will be summarized using an exact score test through logistic regression using the randomization strata and treatment group in the model specification. Missing values for proportion endpoints will not be imputed and will be assumed to be failures. Additional covariates may be specified in the SAP.

9.4.3 Analysis of the Secondary Efficacy Endpoints

The analysis population for the Secondary Efficacy Endpoint analyses is the ITT analysis set, including all classic CAH subjects who were randomized into the study.

Table 7. Secondary Efficacy Endpoints

Objectives	Endpoints		Analysis
Secondary Efficacy			
To evaluate the effect of tildacerfont in reducing GC use to near-physiologic levels while maintaining androgen control in subjects with CAH	2.1	Proportion of subjects with GC dose $\leq 11 \text{ mg/m}^2/\text{day}$ in HCe and $A4 \leq 1.2 \times \text{baseline}$ or $A4 \leq \text{ULN}$ at Week 24	Primary Analysis
To evaluate the effect of tildacerfont in reducing GC use to near-physiologic levels while maintaining androgen control in subjects with CAH	2.2	Proportion of subjects with baseline GC dose $\leq 35 \text{ mg HCe}$ who achieve GC dose $\leq 11 \text{ mg/m}^2/\text{day}$ in HCe and $A4 \leq 1.2 \times \text{baseline}$ or $\leq \text{ULN}$ at Week 24	Primary Analysis
To evaluate the effect of tildacerfont in reducing cardiovascular risk in subjects with CAH	2.3	Proportion of subjects with improvement in at least one cardiovascular risk factor at Week 24	Primary Analysis

For Secondary Efficacy Endpoint 2.1 the null hypothesis is that the difference between randomized treatment groups in the proportion of subjects achieving GC dose $\leq 11 \text{ mg/m}^2/\text{day}$ in HCe and $A4 \leq 1.2 \times \text{baseline}$ or $A4 \leq \text{ULN}$ at Week 24 is equal to zero. The alternative hypothesis is that the difference is not equal to zero.

For Secondary Efficacy Endpoint 2.2 the null hypothesis is that in the subset of subjects with a baseline GC dose $\leq 35 \text{ mg}$ the difference between randomized treatment groups in the proportion of subjects achieving GC dose $\leq 11 \text{ mg/m}^2/\text{day}$ in HCe and $A4 \leq 1.2 \times \text{baseline}$ or $A4 \leq \text{ULN}$ at Week 24 is equal to zero. The alternative hypothesis is that the difference is not equal to zero.

Secondary Efficacy Endpoint 2.3 is the proportion of classic CAH subjects who were randomized into the study who improve at least one baseline CV risk factor at 24 weeks from randomization. This proportion is calculated for each treatment group (e.g., placebo, tildacerfont) as the number of subjects at Week 24 who had at least one CV risk factor at baseline (i.e. subjects without any CV risk factors will not be included in the analysis) and no longer meets one or more of the baselines CV risk factors at Week 24, divided by the total number of subjects in the ITT analysis who were randomized to that specific treatment and had at least one CV risk factor at baseline.

Additional details on secondary endpoints and analysis may be specified in the SAP.

9.4.4 Analysis of the Exploratory Efficacy Endpoints

The analysis population for Exploratory Efficacy Endpoint analyses is the ITT analysis set, including all classic CAH subjects who were randomized into the study. Detailed information around the analysis of the exploratory endpoints listed in [Section 3](#) is provided in the Statistical Analysis Plan (SAP) Version 1.0.

9.4.5 Analysis of the Exploratory Efficacy Endpoints in the Optional Extension Period

Analysis of the Exploratory Efficacy Endpoints in the Optional Extension Period is not included in the SAP Version 1.0, as it will be described in a separate SAP not yet developed and, therefore, is not addressed herein.

9.4.6 Analysis Evaluation Periods

The primary evaluation period will evaluate baseline to Week 24 comparing the tildacerfont group to the placebo group. Select endpoints will also be evaluated using the following periods:

- After 52 weeks on tildacerfont treatment (Week 52 for the tildacerfont group and Week 76 for the placebo group compared to baseline)
- After approximately 24 weeks on tildacerfont treatment (Week 24 for the tildacerfont group and Week 52 for the placebo group compared to Week 24 for the placebo group)
- After 76 weeks on tildacerfont treatment (Week 76 for the tildacerfont group compared to baseline)
- From baseline to Week 76
- From baseline to EOT

The baseline for each evaluation period will be defined in the SAP.

9.4.7 Safety Analyses

The Safety Population will be used for all safety analyses. All safety data will be presented in listings. Summary tables will be provided for concomitant medications, AEs, hematology and chemistry laboratory results, vital signs, and ECG findings. Safety data will be summarized by treatment group using frequency of event or descriptive statistics, as appropriate.

9.4.7.1 Extent of Exposure

Dosing information for individual subjects will be listed. Using dosing data, estimates of exposure to tildacerfont will be summarized. Dose discontinuations and reasons for study drug discontinuation will be listed and summarized.

9.4.7.2 Concomitant Medication Data

Concomitant medications used before and during the Treatment Period will be summarized.

9.4.7.3 Adverse Event Data

AEs will be coded using the Medical Dictionary for Regulatory Activities (MedDRA). AE summaries will be presented by System Organ Class, Preferred Term, severity, and frequency and percentage of subjects reporting each observed event.

AEs that occur before the first dose of study drug will be distinguished from TEAEs (defined in [Section 8.3.1](#)). All AEs and TEAEs will be listed by subject. The frequency of subjects who experience TEAEs will be summarized overall and by treatment group. TEAEs will also be summarized by relationship to study drug and severity.

Listings will be provided for subjects who experienced an SAE or discontinued study drug/withdrew from the study because of an AE.

9.4.7.4 *Laboratory Data*

Clinical laboratory test results will be listed by subject. Reference ranges provided by the laboratory for each parameter will be used to evaluate the clinical significance of laboratory test results. Values outside the relevant reference range will be flagged in the listings. Abnormal clinical laboratory test results will be listed in a separate listing.

Laboratory data will be summarized in terms of observed values, changes from baseline, values relative to normal ranges, and changes from baseline relative to normal ranges. Subjects meeting specific thresholds for laboratory data will also be summarized as specified in the SAP.

P-values for change from baseline and change from placebo or differences in proportions meeting specific thresholds will be derived using the appropriate statistical test as specified in the SAP.

Additional subgroup analyses based on baseline laboratory data [elevated, normal] will be specified in the SAP.

9.4.7.5 *Vital Signs Data*

Vital signs data will be summarized within appropriately defined categories in terms of observed values (by time point), changes from baseline (by time point), and counts and percentages. Subjects meeting specific thresholds for vital sign data will also be summarized as specified in the SAP.

P-values for change from baseline and change from placebo will be derived using t-tests as specified in the SAP.

9.4.7.6 *ECG Data*

The QTcF, PR interval, QT interval, QRS duration, and heart rate from standard digital ECGs will be summarized within appropriately defined categories in terms of observed values, changes from baseline, and counts and percentages.

9.4.7.7 *Psychiatric Evaluations*

C-SSRS and HADS data will be listed.

9.4.8 Baseline Descriptive Statistics

Demographics and baseline characteristics (including age, sex, race, ethnicity, height, weight, and BMI) will be summarized for the ITT Population.

Biomarkers at screening and at baseline will be summarized for the Safety Population.

Baseline clinical characteristics and history will be summarized.

9.4.9 Subgroup Analyses

The following pre-defined subgroups will be analyzed:

- Baseline GC formulation [HC mono therapy, prednisolone/prednisone/methylprednisolone monotherapy, combination therapy]
- Baseline HCe dose [<40 mg/day, ≥40 mg/day], [<35, ≥35 mg/day]

- Sex [male, female]
- A4 ULN at baseline [\leq ULN, $>$ ULN]

The subgroups will be used in supportive analysis of the primary endpoint and secondary endpoints, as applicable. Any additional subgroup analyses will be specified in the SAP.

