8.2 Presentation of p-values

Results of statistical analyses will be reported using summary tables, listings, and figures (TLFs). The ICH of Technical Requirements for Pharmaceuticals for Human Use numbering convention will be used for all TLFs. The following conventions will be followed:

Unless otherwise noted, all statistical testing will be two-sided and will be performed at the 0.05 significance level. Tests will be declared statistically significant if the calculated p-value is < 0.05 , unless otherwise specified. P-values will be reported with 4 significant digits except when reporting p-values less than 0.001, reported as < 0.001 .

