9.7 Examination of Subgroups

Subjects will be categorized into the following common subgroups for the purposes of evaluating the Primary and Secondary Efficacy Endpoints.

- Sex (Male, Female)
- Baseline GC dose in HCe
 - < 40 mg/day, \geq 40 mg/day
 - < 35 mg/day (For endpoint 2.2 and 3.7 only)
- Baseline A4 levels (A4 \leq ULN, A4 $>$ ULN)

In addition, all potential subgroup x subgroup combinations are also pre-specified. If the primary analysis is positive, exploratory subgroup analysis for age, race, ethnicity, and region will be used to further evaluate the Primary and Secondary Efficacy endpoints.

Comparisons will only be provided for subgroups where each subgroup has at least 10 subjects. Additional subgroups specific to only select endpoints are specified in the appropriate section in the SAP.

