12.4.2 Subgroup Analyses

The Primary Efficacy Endpoint Analysis will be repeated using the planned subgroups, by Sex, by Baseline GC dose, by Baseline GC type, by Baseline A4 ULN group.

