12.5.2 Subgroup Analyses

Subgroup analyses for Secondary Efficacy Endpoints 2.1, 2.2 and 2.3 will be performed using the planned subgroups, by Sex, by Baseline GC dose, by Baseline GC type, by Baseline A4 ULN group.

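### Subgroup results come from separate p<0.05 analyses inside each subgroup and each subgroup-by-subgroup cell, with no treatment-by-subgroup interaction, so they cannot show whether the effect differs.

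*Protocol*

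**What the plan says.** Protocol 9.4.9 lists baseline GC formulation, baseline HCe dose (cuts at 40 and 35 mg/day), sex and baseline A4 relative to the ULN. It describes their use as supportive: "The subgroups will be used in supportive analysis of the primary endpoint and secondary endpoints, as applicable". It says nothing about refitting models or crossing factors. The method is in the SAP.

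- **SAP 12.4.2:** "The Primary Efficacy Endpoint Analysis will be repeated using the planned subgroups, by Sex, by Baseline GC dose, by Baseline GC type", and also by baseline A4 group.
- **SAP 12.5.2:** "Subgroup analyses for Secondary Efficacy Endpoints 2.1, 2.2 and 2.3 will be performed using the planned subgroups", with the same four factors.
- **SAP 9.7:** lists sex, baseline GC dose and baseline A4, but not GC type. It then states: "In addition, all potential subgroup x subgroup combinations are also pre-specified". The size limit is: "Comparisons will only be provided for subgroups where each subgroup has at least 10 subjects". Whether the 10 is a total or a per-arm count is not stated.
- **SAP 8.2:** "Unless otherwise noted, all statistical testing will be two-sided and will be performed at the 0.05 significance level". It adds: "Tests will be declared statistically significant if the calculated p-value is < 0.05 , unless otherwise specified". No section exempts subgroups.
- **SAP 12.3.3:** the only interaction in the primary MMRM is treatment by visit. No treatment-by-subgroup term appears elsewhere.
- **SAP 9.6 and Protocol 9.6:** error control covers the primary and secondary endpoints. Subgroups lie outside it.

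**The concern.** A subgroup analysis should say whether the treatment effect varies with a baseline characteristic. Repeating the main analysis inside each level answers another question: whether the effect differs from zero there, with a fraction of the subjects. A significant result in one level beside a non-significant one in the other invites the conclusion that the drug works only in the first. The two p-values do not support that conclusion, because no comparison between levels has been made.

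Crossing the factors multiplies the number of such tests and shrinks the cells. Under a default p<0.05 rule, some cells will look positive by chance. SAP 9.7 defers only age, race, ethnicity and region to a positive primary result. The core subgroups and their combinations are analysed whatever the primary shows, including after a null result, when a pre-specified significant subgroup is most open to over-reading.

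**Working it through.** **Inputs from the documents.** About 90 subjects, 1:1, so 45 per arm (Protocol 5 and 6.3). Two-sided alpha 0.05 (SAP 8.2). Planning values from SAP 6: 5 mg/day with SD 6.9, and 7.25 mg/day with SD 10.5.

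**Assumptions.** The documents give no subgroup prevalences. Factors are taken as independent and split 50/50, then varied up to 65/35. A two-sample t-test stands in for the Week 24 MMRM contrast.

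**Step 1: the SAP's own power figures.** Power = Φ(δ/SE − 1.96), with SE = SD√(2/n).
- 7.25 mg/day, SD 10.5, n=45: SE = 2.214, ratio 3.275, power 90.6%.
- 5 mg/day, SD 6.9, n=40: SE = 1.543, ratio 3.241, power 90.0%.

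Both stated figures of at least 90% reproduce. The documents state no error rate for the subgroup analyses.

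**Step 2: same effect in both levels of one factor.** Each level holds 45/2 = 22.5 subjects per arm. With power p in each level, the chance that exactly one level is significant is 2p(1 − p). Power is from the noncentral t with 43 df.

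| Effect, SD (mg/day) | SE | p | 2p(1 − p) |
|---|---|---|---|
| 5, 6.9 | 2.06 | 66% | 45% |
| 7.25, 6.9 | 2.06 | 93% | 13% |
| 7.25, 10.5 | 3.13 | 62% | 47% |

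Simulation of the first row gave 45.4%. An interaction test of the same factor was positive in 4.9%, as its 5% level implies.

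**Step 3: no drug effect anywhere, primary endpoint.** Three two-level factors give 6 levels plus 3 × 4 = 12 pairwise cells, or 18 tests. Four factors give 8 + 6 × 4 = 32 tests. The independence formula 1 − 0.95^k gives 60.3% and 80.6%. These are too high, because the subgroups share subjects. Simulation at N=90 allows for the overlap. Chance of at least one p<0.05:

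| Subgroups analysed | At least 10 in total | At least 10 per arm |
|---|---|---|
| Single factors only, three factors | 22% | 22% |
| Single factors only, four factors | 25–26% | 25–26% |
| Plus pairwise cells, three factors of SAP 9.7 | 41–42% | 31–33% |
| Plus pairwise cells, GC type added | 56–57% | 40–43% |
| As above, three-level GC formulation of Protocol 9.4.9 | 60% | 38% |

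**Step 4: the same, given a non-significant primary result.** With pairwise cells, a chance p<0.05 that favours the drug appears in about 21% (total) or 15% (per arm) of trials with three factors. With four factors it is about 31% or 21%.

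**Step 5: what an interaction analysis delivers.** For a two-level factor split 50/50, SE of the interaction = 6.9√(4/22.5) = 2.91 mg/day. Power for a 5 mg/day interaction = Φ(5/2.91 − 1.96) = Φ(−0.24), about 40%. The 95% CI half-width is 1.96 × 2.91 = 5.7 mg/day. The chance of at least one false interaction is 1 − 0.95³ = 14.3% for three factors and 1 − 0.95⁴ = 18.5% for four.

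**The case against.** The strongest reply is that nothing confirmatory depends on these analyses. The protocol calls them supportive, the multiplicity scheme covers only the primary and secondary endpoints, and SAP 8.2 is a general reporting convention. No subgroup section says that an effect will be declared from it. SAP 12.7 already allows forest plots. All of that stands, and it limits the point to interpretation. It does not supply a test of whether effects differ, and a general rule that exempts nothing still applies.

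The size also depends on assumptions. The 45% falls to 13% if the effect is 7.25 mg/day with SD 6.9. Interaction tests are themselves weak here, and several of them would produce some false positives. These objections stand too, and are why ranges are given and CIs preferred to interaction p-values.

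A reader might infer three stronger things that the documents do not support.

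- **A false-positive subgroup is more likely than not.** For the primary endpoint with pairwise cells, this needs GC type to be crossed, although SAP 9.7 omits it from the list that the crossing sentence follows, and also needs the limit of 10 to be a total. On the SAP 9.7 list the figure is 31% to 42%. Counting the three secondary endpoints as well gives 55% to 73%, but only with assumed response rates of 20% to 40%, assumed correlations of 0.3 to 0.7, and all subjects in every test, although endpoints 2.2 and 2.3 use subsets.
- **A failed trial would probably yield a rescue subgroup.** Given a non-significant primary result, a chance finding in the drug's favour has a probability of about 15% to 31%.
- **The MMRM cannot be fitted in small cells.** SAP 12.3.3 provides simpler covariance structures if the unstructured one does not converge.

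**Conclusion.** The point holds as a weakness of method and reporting. The planned subgroup analyses cannot answer whether the treatment effect varies, because no interaction is estimated. With a uniform effect, one factor gives a misleading split in about 45% of trials at 5 mg/day and SD 6.9, within a range of 13% to 47%. With no effect, the chance of at least one p<0.05 on the primary endpoint is about 30% to 60% once pairwise cells are included. Where it falls in that range turns on two matters the SAP leaves open: whether GC type is crossed, and whether the minimum of 10 is total or per arm. These figures rest on N=90, assumed and independent subgroup splits, and a t-test in place of the MMRM contrast. The type I error of the primary claim is unaffected. The change should be made, but the trial's main conclusion does not depend on it.

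**What to change.** Amend SAP 9.7, 12.4.2 and 12.5.2, and add an exemption in SAP 8.2:

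1. For each factor, fit one model on the full ITT set. Add treatment × subgroup × visit with its lower-order terms to the MMRM, and treatment × subgroup to the logistic models.
2. Report the Week 24 effect in each level and the interaction estimate, each with a 95% CI, preferably in a forest plot.
3. State that SAP 8.2's significance rule does not apply to subgroups, and give no within-subgroup p-values.
4. Show two-way cells descriptively only.
5. State whether the minimum of 10 subjects is total or per arm.
6. Reconcile GC type, which is absent from SAP 9.7 but present in 12.4.2 and 12.5.2.

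The cost is SAP wording, with fewer models to run. The downside is imprecision: at N=90 an interaction of 5 mg/day would be detected only about 40% of the time, and the intervals will be wide. The CIs show that openly, whereas separate p-values conceal it.

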9.5 Primary and Final Analyses

The primary efficacy analysis is planned after all subjects have completed Week 24, at the end of the double-blind treatment period.

The final analyses will occur after the last subject has completed the follow-up visit after Week 76 or if the study is discontinued by the Sponsor.

A clinical study report will be completed for the study with results up to Week 76/80. An addendum to the clinical study report will be completed to summarize results from Week 76 up to Week 316/320.

